### 9.1 Data to be collected Baseline

#### characteristics

Date of ICU admission

Age

Sex

SAPS3-score on arrival to the ICU SOFA-

score on arrival to the ICU Presence of:

Liver cirrhosis (defined as Child-Pugh-score  $\geq$ A)

Heart failure (defined as ejection fraction  $<$ 40%)

Diabetes mellitus (not diet treated)

Renal failure (defined as creatinine clearance  $<$ 30 mL/min/1.73m^2)

Body Mass Index  $>$ 30 kg/m^2

Haematological malignancy

Hematopoietic stem cell transplantation

Organ transplantation

Daily smoking in the last year

Solid tumour

Neutropenia (defined as  $<$ 0,5 x10^9 neutrophils)

Chronic obstructive pulmonary disease

New lung infiltrate

Treatment with corticosteroids in the last 28 days

Treatment with corticosteroids in a dose equal to or above 15 mg/day prednisone

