#### At enrolment

Date of enrolment

Influenza A or B

Treatment with oseltamivir or zanamivir

SOFA-score the day of enrolment

Use of vasopressor

Use of continuous renal replacement therapy

Use of invasive ventilation

Use of non-invasive ventilation  
Body temperature above 38.0 degrees Celsius in the last 24 hours  
ARDS grade (defined by PaO2/FiO2 300-200 mmHg mild, 200-100 mmHg moderate, <100 mmHg severe) Treatment with corticosteroids  
Presence of haemoptysis  
Presence of pleural pain  
Ongoing treatment with antibiotics  
Ongoing treatment with antifungals

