#### **Daily registration after enrolment**

SOFA-score  
Use of vasopressor  
Use of continuous renal replacement therapy  
Use of invasive ventilation  
Use of non-invasive ventilation  
Body temperature above 38.0 degrees Celsius in the last 24 hours ARDS grade (defined by PaO2/FiO2 300-200 mmHg = mild, 200-100 mmHg = moderate, <100 mmHg = severe)  
Treatment with corticosteroids  
Presence of haemoptysis  
Presence of pleural pain  
Ongoing treatment with antibiotics  
Ongoing treatment with antifungals

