## **11 STUDY ENDPOINTS**

Enrolled patients will be categorized as proven or probable IPA at discharge from the ICU to answer the primary objective of evaluating the prevalence of influenza related invasive pulmonary aspergillosis. A modified version of the Asp-ICU criteria will be used, described below 11.1, 11.2.

All recorded baseline characteristics will be compared between patients diagnosed with IPA and those that were not. The following outcome parameters will also be assessed: SOFA-score, use of mechanical ventilation, use of non-invasive ventilation, use of vasopressor, use of renal replacement therapy, ARDS-grade using the Berlin definition, median number of ICU stay, ICU mortality, and 90-day mortality after ICU admission.

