## **12 STATISTICAL ANALYSIS**

Prevalence of Proven/Probable IPA will be calculated at the 95% confidence level. Patients meeting the criteria for proven/probable IPA will be compared to the influenza positive patients who do not meet the criteria, in terms of underlying risk factors and outcome measures. Categorical variables will be assessed by Fischer exact test and  $X^2$  test, and continuous variables with t-test or Mann Whitney U test where appropriate. We will also perform multivariable analysis by binary logistic regression to detect independent risk factors for IPA. All analyses will be conducted using a threshold of 95% confidence level (P-value 0.05). ICU mortality and 90 days after admission to the ICU mortality will be compared using survival analysis.

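### SOFA as an outcome is compared between IPA and non-IPA patients without using the SOFA score on ICU arrival, so a difference already present on arrival could be read as clinical impact of IPA

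*Combined protocol and SAP*

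**What the plan says.** Section 11 first says that baseline characteristics will be compared between the groups, and then adds: "The following outcome parameters will also be assessed: SOFA-score, use of mechanical ventilation", followed by further outcomes. SOFA is therefore an outcome as well as a baseline item. No time point or summary (peak, mean, change) is given for it.

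Section 9.1 records SOFA at three stages:
- among the baseline characteristics, on ICU arrival ("SAPS3-score on arrival to the ICU SOFA", where the SOFA item continues on the next line of the extracted text);
- at enrolment ("SOFA-score the day of enrolment");
- each day under the heading "Daily registration after enrolment".

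Section 12 compares patients with proven or probable IPA with the remaining influenza patients, on risk factors and on outcomes, and assigns "continuous variables with t-test or Mann Whitney U test where appropriate". It does not name SOFA; the general rule for continuous variables applies by default. The one multivariable model is "multivariable analysis by binary logistic regression to detect independent risk factors for IPA", so IPA is its dependent variable. Survival analysis is reserved for mortality.

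Section 6.2 gives SOFA two roles: the secondary objective covers clinical impact, and SOFA is also named among the data to be examined for risk factors.

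**The concern.** IPA and non-IPA patients are formed by diagnosis, not by randomisation, and may differ in organ failure when they reach the ICU. An unadjusted comparison of a later SOFA score then mixes two things: the difference the groups brought with them, and any divergence afterwards. Only the second can be called impact after arrival. Because the plan treats SOFA both as a possible risk factor and as an outcome, a reader of the results could not tell the two apart from the planned test.

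A smaller, separate matter is precision. If the groups are alike on arrival, the arrival score still explains part of the variation in the later score, and a test that ignores it loses power. The expected IPA group is small, about 8 patients at the minimum enrolment.

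**Working it through.** **The plan's own figure.** Section 7.2 gives a minimum of 50 patients from 15% prevalence and a 10-point margin at 95% confidence. The Wald formula gives 1.96² x 0.15 x 0.85 / 0.10² = 48.98, rounded up to 49. At n = 50 the half-width is 1.96 x sqrt(0.15 x 0.85 / 50) = 9.9 points. The figure reproduces. It concerns prevalence only; no power is stated for SOFA.

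**Inputs from the documents.**
- Group sizes: 15% of 50 is 7.5, taken as 8 v 42. With the roughly 100 influenza admissions per season in section 7.2, 15 v 85.
- Significance level 0.05 (section 12), taken as two-sided because sidedness is not stated.

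**Assumptions, because the documents give no values.**
- Correlation rho between arrival and later SOFA: 0.3, 0.5, 0.7.
- Arrival difference D: 0.5 SD, with 1 SD as a wider case.
- A true later difference of 0.8 SD for the power illustration.

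**Carry-over when IPA has no effect after arrival.** In SD units the expected later difference is rho x D. The standard error is sqrt(1/n1 + 1/n0): 0.386 at 8 v 42 and 0.280 at 15 v 85. The chance of p < 0.05 comes from the noncentral t distribution with noncentrality rho x D / SE.

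| D = 0.5 SD | rho 0.3 | rho 0.5 | rho 0.7 |
|---|---|---|---|
| Carried-over difference (SD) | 0.15 | 0.25 | 0.35 |
| Significant at 8 v 42 | 6.7% | 9.7% | 14.4% |
| Significant at 15 v 85 | 8.3% | 14.3% | 23.6% |

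For D = 1 and rho = 0.5 the figures are about 25% and 42%. The chance rises with sample size, because the carried-over difference stays the same while the standard error shrinks.

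**Power when arrival scores are balanced (a different scenario).** Adjustment multiplies the residual variance by 1 - rho² (0.91 / 0.75 / 0.51) and costs one degree of freedom.

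| True difference 0.8 SD | Unadjusted | rho 0.3 | rho 0.5 | rho 0.7 |
|---|---|---|---|---|
| 8 v 42 | 53% | 57% | 65% | 81% |
| 15 v 85 | 81% | 84% | 90% | 98% |

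**Effect of imbalance on that gain.** Correlation between group and arrival score inflates the adjusted variance by about 1 + 0.15 x 0.85 x D². At D = 1 this is 1.1275, so the adjusted-to-unadjusted variance ratio at rho = 0.3 is 0.91 x 1.1275 = 1.03 and the gain is gone. At rho = 0.5 the ratio is 0.75 x 1.1275 = 0.85.

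**When adjustment works the other way.** Suppose IPA is already present on arrival and itself causes D = 0.5 there, with a total later difference of 0.8 SD and rho = 0.5. The adjusted difference is 0.8 - 0.5 x 0.5 = 0.55 SD. At 8 v 42 power falls from 53% unadjusted to about 36% adjusted.

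**The case against.** The strongest objection is that adjustment is not automatically the better analysis. IPA status is assigned at ICU discharge, and influenza may be diagnosed up to 7 days before admission, so some IPA may already be present on arrival. In those patients arrival SOFA is partly a consequence of IPA, and conditioning on it removes part of the impact, as the last calculation shows. This stands. It is the reason to show both estimates and to limit what the adjusted one is said to mean.

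Second, the SOFA outcome is not defined, and daily SOFA is recorded only during the ICU stay, so any summary is cut short by death or discharge. A covariate does not solve that. This also stands, and the outcome has to be defined before a model can be specified.

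Third, a reader might infer that the 7 to 24% is an inflated type I error. It is not. The null hypothesis of the unadjusted test is equal SOFA in the two groups; if the groups differ, rejecting it is correct. The error would lie in attributing the difference to IPA.

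Fourth, a reader might infer that the plan suffers both bias and loss of power. The documents do not support that: the carry-over figures assume an arrival imbalance, the power figures assume none, and neither scenario has documented inputs. Nor does naming SOFA among possible risk factors show that an imbalance is to be expected.

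Finally, the planned comparison of baseline characteristics would display arrival SOFA by group. That makes an imbalance visible but does not remove it from the outcome comparison, and with about 8 IPA patients a test could easily miss one.

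**Conclusion.** The point holds in a limited form. The plan compares SOFA as an outcome between non-randomised groups with an unadjusted test, although the arrival score is available, and a difference on arrival could then be reported as clinical impact of IPA.

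How much this matters cannot be determined from the documents. The carry-over figures are illustrations under the stated assumptions. The precision gain is conditional as well: about 4 points at rho 0.3 and about 12 at rho 0.5 (8 v 42, 0.8 SD, balanced arrival scores), and it can vanish with a large imbalance. No stated figure in the plan is wrong, since no power was planned for this comparison.

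This is a minor improvement to one secondary comparison. The prevalence estimate, which is the primary objective, is unaffected.

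**What to change.** In section 12:

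1. Define one SOFA outcome over a fixed window that is the same for all patients, for example the highest daily SOFA in a stated number of days after enrolment.
2. State how death and ICU discharge within the window are handled.
3. Report a linear model of that outcome on IPA group with SOFA on ICU arrival as covariate, giving the adjusted difference with its 95% CI beside the unadjusted difference.
4. State that the adjusted estimate describes worsening after arrival only, because in patients whose IPA is already present on arrival the adjustment removes part of its impact.

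The cost is a short paragraph and one model with a single covariate. No new data are needed, since all the scores are already in section 9.1. The real work is in items 1 and 2, which the unadjusted comparison needs as well. With about 8 IPA patients at the minimum enrolment, few further covariates could be supported.

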## 5. INTRODUCTION: BACKGROUND INFORMATION AND SCIENTIFIC RATIONALE

### 5.1 Background

Bacterial pneumonia is a well-known complication of influenza infection and contributes to both increased morbidity and mortality. A less known complication is a fungal infection with aspergillus species. Aspergillus is omnipresent and is commonly found in soil, dust, and food. We regularly inhale Aspergillus spores, but our immune system effectively takes care of the fungus, why disease does not occur [2]. Invasive pulmonary aspergillosis (IPA) has typically only been considered in immunosuppressed patients such as in haematological malignancies, hematopoietic stem cell transplantation, organ transplantation, or prolonged neutropenia [3]. Isolation of Aspergillus in respiratory samples from patients without these risk factors has been interpreted as colonization without any clinical relevance.

In recent years, several reports of influenza-related IPA in patients lacking classical risk factors have been published [4,5]. A possible explanation could be a viral injury to the respiratory epithelium as well as local and systemic lymphopenia [6]. The prevalence of IPA in influenza patients admitted to the ICU has been reported to be upwards of 23% [4]. In a large retrospective cohort study from the Netherlands and Belgium, published in The Lancet in October 2018, the prevalence of IPA was 19% among the 432 influenza patients admitted to the ICU [10]. The mortality was significantly higher among patients diagnosed with IPA. Most patients with influenza admitted to ICU lack classical risk factors for IPA and have, therefore, not been routinely investigated for IPA.

Aspergillus infections are challenging to diagnose and require specific culture media or the use of indirect diagnostic methods such as detection of Galactomannan in serum or BAL and detection of Beta-D-Glucan in serum. However, microbiological tests cannot distinguish between colonization and infection, which is why internationally recognized criteria that combine host factors, radiological signs, and microbiological findings have been published [7]. The infection is graded being confirmed, probable, or possible IPA. The criteria were originally developed for immunosuppressed patients, but modified criteria that are useful in the ICU has been published [8].

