### **6.2 Secondary objective**

To assess the clinical impact and risk factors related to influenza-related invasive pulmonary aspergillosis. Patients with proven or probable IPA will be compared to patients that do not meet the criteria for proven and probable IPA. Baseline characteristics and clinical data such as SAPS3, SOFA score, need for invasive ventilation and need for continuous renal replacement therapy, will be assessed to find risk factors for IPA.

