## **7. STUDY DESIGN**

### **7.1 Study overview**

The study is a Swedish, nationwide, multicenter, prospective observational cohort study to determine the prevalence of IPA among patients admitted to the ICU with confirmed influenza infection.

A new clinical routine regarding IPA-testing will be implemented at the participating centers, similar to the current guidelines in the Netherlands. All samples will be retrieved and analyzed using local methods and logistics. All test results will be available to the patient responsible physician, who is free to act on them as deemed appropriate.

The study is non-interventional, no measurements or sampling will be made mandatory by the protocol and data collection at these pre-specified time-points will only take place if decided acceptable by the patient responsible physician. All aspergillus testing is part of the new clinical routine, and no additional sampling will be performed on accounts of the study.

All patients  $\geq 18$  years of age with confirmed influenza A or B diagnosed up to 7 days before ICU admission, or during ICU care, will be included in the study. Patient consent was waived in the ethics approval from *the Swedish Ethical Review Authority* (Dnr 201900557).

Recruitment is planned to begin in December 2019. Recruitment of patients is expected to stop in April 2020 if  $\geq 50$  patients have been recruited, or after that when 50 patients have been recruited.

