### **7.2 Study inclusion**

At least 50 patients will be enrolled in the study. The target sample size has been calculated using the expected prevalence of 15% IPA. The sample size is then sufficient to describe the prevalence with 10 % margin of error at the 95% confidence level. Approximately 100 influenza patients are admitted to ICUs of the participating centers every influenza season.

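### The logistic model for IPA risk factors has no covariate limit and no method for separation, with about 7.5 cases expected at 50 patients and about 15 at 100

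*Combined protocol and SAP*

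**What the plan says.** Section 12 describes the adjusted analysis in one sentence: "We will also perform multivariable analysis by binary logistic regression to detect independent risk factors for IPA". It then sets a common threshold: "All analyses will be conducted using a threshold of 95% confidence level (P-value 0.05". It names no covariates, maximum number, selection rule, type of test or interval, or procedure for sparse data. Fisher's exact test is listed, but only for the unadjusted comparison of categorical variables.

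Candidates appear elsewhere, as an open list. Section 6.2 says: "Baseline characteristics and clinical data such as SAPS3, SOFA score, need for invasive ventilation and need for continuous renal replacement therapy, will be assessed". Section 11 compares every baseline item between the groups; section 9.1 lists 19 of these besides the admission date. Several could be rare, such as stem cell transplantation and neutropenia.

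Two features of that list bear on the model:

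- SOFA, ventilation and renal replacement are risk-factor candidates in section 6.2 and outcome parameters in section 11. Section 9.1 records them at enrolment (for example "Use of continuous renal replacement therapy") and again daily. The plan does not say which value enters the model.
- New lung infiltrate is a baseline item in section 9.1, while section 11.2 makes an infiltrate on imaging a condition for probable IPA.

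The sample size was set for the prevalence alone. Section 7.2 states: "The target sample size has been calculated using the expected prevalence of 15% IPA". It adds: "Approximately 100 influenza patients are admitted to ICUs of the participating centers every influenza season". Section 7.1 says "Recruitment of patients is expected to stop in April 2020" if 50 patients have been enrolled by then, and otherwise when the fiftieth is enrolled.

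**The concern.** For a binary outcome, the information in a logistic model is governed mainly by the smaller outcome group, here the IPA cases. With seven or eight cases, a covariate of moderate frequency can easily be absent from all of them. Maximum likelihood then pushes the log odds ratio to infinity and the Wald interval is unusable. Fits that do converge can still give exaggerated odds ratios.

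At stake is what the study can say about independent risk factors. With some 20 candidates, no pre-set limit and a 0.05 threshold, the reported model could depend on choices made after the data are seen. A daily SOFA or renal-replacement value recorded after IPA began could be reported as a risk factor when it is a consequence. A variable that overlaps the case definition could appear as a predictor of it.

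**Working it through.** **The plan's own figure.** For 15% prevalence and a 10-point margin, n = 1.96² × 0.15 × 0.85 / 0.10² = 48.98, so 49. The stated 50 is reproduced, and it addresses prevalence only.

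**Expected cases.** Prevalences are 15% (section 7.2) and, as a high value, 23% (section 5.1: "The prevalence of IPA in influenza patients admitted to the ICU has been reported to be upwards of 23" per cent). Ranges are binomial 2.5-97.5% quantiles.

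| Patients | 15% | 23% |
|---|---|---|
| 50 | 50 × 0.15 = 7.5 (3-13) | 50 × 0.23 = 11.5 (6-18) |
| 100 | 100 × 0.15 = 15 (8-22) | 100 × 0.23 = 23 (15-31) |

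At 50 patients and 15%, the chance of fewer than 5 cases is 11%.

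**One binary covariate unrelated to IPA.** With covariate frequency q, the chance that no case carries it is (1 − 0.15q)ⁿ. For q = 20% this is 0.97⁵⁰ = 22% and 0.97¹⁰⁰ = 5%. For q = 10% it is 0.985⁵⁰ = 47% and 0.985¹⁰⁰ = 22%.

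**Whole models.** Separation, complete or quasi-complete, was checked by linear programming in simulated samples, mostly 1,000 to 2,000 per setting, at 15% prevalence unless stated. Covariate frequencies and effects are assumptions; none is in the document. The four section 6.2 variables were taken as two standard-normal scores, ventilation at 50-55% and continuous renal replacement at 15-25%.

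| Model | n = 50 | n = 100 |
|---|---|---|
| Four variables, no effects | 18-35% | 2-11% |
| Four variables, no effects, 23% prevalence | 5-17% | 0.3-3% |
| Four variables, odds ratio 3 for both binaries | 14-24% | 1.5-3% |
| Four variables, odds ratio 3 for renal replacement only (two runs) | 7% and 10% | 0.4% and 0.3% |
| Five covariates, some at 8-15%, no effects | 68-82% | 30-47% |
| Same five, odds ratio 3 for three of them | 52-66% | 13-29% |
| Three binaries at 20%, odds ratio 1 or 3 | 41-50% | 9-12% |
| Three binaries at 30-40%, odds ratio 1 or 3 | 17-25% | 1.4-2.3% |
| Two binaries at 40%, odds ratio 1 or 3 | 10-11% | 0.4-0.6% |

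A pairwise latent correlation of 0.5 among the four variables hardly changed the no-effect figures (19-36% and 2-10%).

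**Quality of the estimates.** Four-variable model, true odds ratio 3 for renal replacement, frequencies 55% and 20%.

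| | n = 50 | n = 100 |
|---|---|---|
| Maximum likelihood, median odds ratio (non-separated fits) | 3.6 | 3.3 |
| Firth, median odds ratio (finite in all samples) | 3.0 | 3.1 |
| Firth, profile-likelihood coverage | 95.5% | 95.5% |
| Firth, power | 23% | 44% |

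At 50 patients, 18% of the non-separated maximum-likelihood estimates were more than tenfold away from 1. At 100 patients the Wald interval also covered in 95%. With only two covariates at 40%, the maximum-likelihood median at 50 patients was 2.89, so the overstatement belongs to the larger model.

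**Testing under separation.** The likelihood stays bounded, so a likelihood-ratio p-value is defined. In the four-variable setting it was finite in every separated sample. Rejection under no effect was 7.8% at 50 patients and 8.5% at 100: somewhat liberal, but usable.

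**The case against.** Four objections carry weight.

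*The test need not fail.* A reader might infer that separation makes the 0.05 decision impossible. The document does not support that: section 12 does not specify a Wald test, and a likelihood-ratio p-value exists. What is lost is the point estimate and any Wald interval.

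*The rates rest on assumptions.* A reader might also infer that the model will usually fail. The four-variable range at 50 patients runs from 7% to 35% depending on assumed frequencies and effects. Section 6.2 does not say that all four variables enter together, and no section puts the five sparser covariates in a model. This stands; the rates show what the open plan permits.

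*Fifty is a floor.* Enrolment continues to April 2020 even after 50 is reached, consent is waived, and about 100 eligible patients per season are expected. Near 100 patients with two or three common covariates, separation is rare and Firth changes little. This also stands, but 50 remains a permitted stopping point. Nor is rare separation the same as precision: at 100 patients with two or three covariates at 30-40%, the 95% interval for an odds ratio still spans about 10- to 13-fold.

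*A cap may remove the adjusted model.* One covariate is not an adjustment. The Firth comparison above used four covariates, which a limit of one per 5 cases would allow only from 20 cases. So most of the gain comes from the limit, and Firth protects what remains.

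On the infiltrate variable, no section says it will enter the model, and proven IPA (section 11.1) does not require an infiltrate. The overlap concerns probable IPA, and nothing excludes the variable.

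**Conclusion.** The concern holds in a graded form. The plan applies an unrestricted logistic model to about 7.5 expected cases at the minimum size and about 15 at the likely upper size. With the four named variables, separation is a material risk at 50 patients (roughly 7-35%) and a small to moderate one at 100 (0.3-11%). Sparse covariates raise it at either size; two or three common ones at 100 patients make it small. In the four-variable setting at 50 patients, converged fits also overstate the odds ratio (median 3.6 for a true 3).

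The case counts follow from the plan's own figures. The separation rates depend on assumed covariate frequencies and effects. The absence of a covariate limit and of any method for separation depends on neither.

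The point does not reach the primary objective: the prevalence estimate and its interval do not use this model. It is a recommended change to the risk-factor part of the secondary objective.

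**What to change.** In section 12, replace the logistic-regression sentence with wording to this effect:

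- The adjusted analysis uses Firth-penalised logistic regression, with profile-likelihood 95% intervals and penalised likelihood-ratio p-values.
- A short list of covariates is chosen and ranked on clinical grounds before data lock, with no screening by p-value.
- Covariates take their baseline or at-enrolment values from section 9.1, not the daily values.
- New lung infiltrate stays out of the model because it overlaps the probable-IPA definition. It is still described by group, so section 11 needs no change.
- The number of covariates is limited by the observed number of cases, for example one per 5.
- Adjusted results are described as exploratory. The sentence applying P 0.05 to all analyses is amended to match, and the exploratory label is carried into sections 3 and 6.2.

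Data collection, sample size and the primary analysis are unchanged.

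The cost is fewer adjusted associations. At one covariate per 5 cases, a model with two covariates needs 10 cases. At 15% prevalence the chance of fewer than 10 is 79% with 50 patients and 6% with 100; only univariable estimates would then be reported. With 15 cases the limit is three covariates, and with 23 it is four. A stricter limit of one per 10 would need 20 cases, and the chance of fewer is 89% even with 100 patients, so the choice of limit should be made with these figures in view.

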#### **At discharge from the ICU**

Date of discharge from the ICU  
Discharge to (home, ward, other ICU or death)  
Treatment with systemic antifungals during the care time in the ICU  
Microbiological findings: Positive Aspergillus culture or microscopy, GM in BAL or serum or Beta-D-Glucan.

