**Radiological criteria:**

Any infiltrate on pulmonary imaging by portable chest x-ray or CT-scan of the lungs.

**Mycological criteria:** One of the following findings:

- Positive microscopy or culture of *Aspergillus* from BAL
- Galactomannan optical index on BAL >0,8
- Galactomannan optical index on serum  $\geq 0,5$

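### The risk-factor analysis does not account for who had a BAL; if ventilated patients have BAL more often, the odds ratio for ventilation is overstated

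*Combined protocol and SAP*

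**What the plan says.** - **Case definition (section 11.2, mycological criteria).** One of three findings is enough: "Positive microscopy or culture of" Aspergillus from BAL; "Galactomannan optical index on BAL >0,8"; or "Galactomannan optical index on serum" of at least 0,5. The first two need a BAL.
- **Sampling (sections 3 and 7.1).** The routine names serum tests twice weekly and one respiratory sample weekly, whose type is not given. Section 7.1 adds that "no measurements or sampling will be made mandatory by the protocol" and leaves sampling to the treating physician. It describes the routine as resembling the Dutch guideline, which section 5.1 summarises as BAL for every influenza patient in the ICU.
- **Candidate risk factors (section 6.2).** "SAPS3, SOFA score, need for invasive ventilation and need for continuous renal replacement therapy, will be assessed to find risk factors for IPA".
- **Analysis (section 12).** Cases "will be compared to the influenza positive patients who do not meet the criteria", and then: "We will also perform multivariable analysis by binary logistic regression to detect independent risk factors for IPA". No covariates are listed. There is no term, restriction or sensitivity analysis for BAL.
- **Data (section 9.1).** The discharge items include "Microbiological findings: Positive Aspergillus culture or microscopy, GM in BAL or serum or Beta-D-Glucan". No item records whether, when or how often BAL was done, or how many serum tests were taken.

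**The concern.** This point concerns the associations in the secondary objective, not the prevalence estimate. A patient who has a BAL can become a probable case by three mycological routes; a patient without one has only serum galactomannan. The chance that a true case is recorded therefore depends on a discretionary procedure. If that procedure is used more often in ventilated patients, the comparison mixes the effect of ventilation on IPA with its effect on being tested. Adjusting for other baseline factors does not separate the two, and enrolling more patients does not shrink the bias.

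As the data items stand, a patient with no BAL and a patient with a negative BAL look alike, so the study could not show afterwards that sampling was balanced. Section 5.2 expects the results to inform national testing guidance, so a risk factor that partly marks who was sampled could steer testing towards those already sampled most.

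**Working it through.** **1. The plan's own figure.** Section 7.2 gives at least 50 patients for 15% prevalence with a 10-point margin at 95% confidence: n = 1.96² × 0.15 × 0.85 / 0.10² = 48.98, so 49. The stated 50 is reproduced. No calculation is given for the risk-factor model. Expected cases at 15% are 7.5 of 50, or 15 of 100 (about one season at the participating centres, section 7.2).

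**2. Inputs for the detection model.** The 15% comes from section 7.2. The rest are assumptions, because the documents give no values: serum galactomannan detects 30–70% of true cases; BAL, when done, detects 70–90%; BAL is done in 50–70% of ventilated and 10–20% of other patients. True IPA is set equal in both groups, so the true odds ratio is 1. The two tests are taken as independent given true IPA, with no false positives.

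**3. Formula.** P(recorded | true IPA) = 1 − (1 − serum sensitivity) × (1 − P(BAL) × BAL sensitivity). Multiply by 15% in each group and take the odds ratio.

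| Setting | Serum | BAL | BAL done, ventilated v other | Detection | Recorded IPA | Odds ratio |
|---|---|---|---|---|---|---|
| Mildest corner | 70% | 70% | 50% v 20% | 0.805 v 0.742 | 12.1% v 11.1% | 1.10 |
| Midpoints | 50% | 80% | 60% v 15% | 0.740 v 0.560 | 11.1% v 8.4% | 1.36 |
| Extreme corner | 30% | 90% | 70% v 10% | 0.741 v 0.363 | 11.1% v 5.4% | 2.17 |

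At the midpoints: (0.111/0.889) / (0.084/0.916) = 1.36. On an even grid over the ranges the median is 1.35, and fewer than 1% of combinations exceed 2. With equal BAL use the two detection probabilities are equal and the odds ratio is 1.00.

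**4. A second set of assumptions.** True IPA 20% in both groups, serum sensitivity 40%, BAL 85%, BAL done in 80% v 20%, half the cohort ventilated. Recorded IPA is 16.2% v 10.0%, odds ratio 1.73. In 400,000 simulated patients the logistic odds ratio for ventilation was 1.74 as planned, 1.01 with BAL performed in the model, and 0.98 with a serum-only endpoint. In this simulation BAL depended only on ventilation; if BAL also follows suspicion of IPA, adjusting for it or restricting to sampled patients would not be as clean.

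**5. Chance of a false finding, same setting.** The probability of p<0.05 in the direction of ventilation is 4% (Fisher) or 10% (chi-square) at N=50, and 8% or 15% at N=100, against about 1% or 3% with equal BAL use.

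**6. Cases left for a serum-based analysis.** At 15% and serum sensitivity 30–70%: 7.5 × 0.3 = 2.25 to 7.5 × 0.7 = 5.25 of 50 patients; 4.5 to 10.5 of 100.

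**The case against.** The strongest objection is that unequal BAL use is not in the documents. No section gives BAL rates by ventilation or severity, and the routine is said to resemble a guideline of BAL for all. The workflow figure in section 8 is missing from the text available and might specify the respiratory sample. If BAL use is equal, the bias is zero. This stands, and it makes the point conditional. It does not remove it: no available text says every patient gets BAL, section 7.1 makes nothing mandatory, and BAL performed is not among the listed data.

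A reader might infer three stronger claims that the documents do not support.

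- *Severity scores and CRRT are biased upward too.* Physicians may withhold BAL from unstable patients, so the sign is uncertain; the calculation covers ventilation only.
- *The bias is always away from 1.* It is upward. With a true odds ratio of 0.5, 20% true IPA in the non-ventilated and detection of 74% v 56%, the recorded value is about 0.71, closer to 1.
- *Ventilation would typically be declared a risk factor through sampling alone.* The 2.2 is an extreme corner, and a false significant result is possible but not usual at 50–100 patients.

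It is also fair that BAL status may be recoverable: section 9.1 lists galactomannan in BAL as a finding and provides for review of records. That makes the fix cheaper but does not put it in the plan.

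**Conclusion.** The concern holds in conditional form. The case definition depends on BAL, BAL is discretionary, ventilation is a named candidate risk factor, and neither the data list nor section 12 accounts for sampling. If BAL is done more often in ventilated patients, the odds ratio for ventilation is overstated: with no true effect, about 1.1 to 2.2 over the assumed ranges and about 1.4 at the midpoints. That size rests wholly on assumed sensitivities and BAL rates. That ventilation enters the logistic model is itself read from section 6.2, since section 12 lists no covariates. For SOFA, SAPS3 and CRRT the plan leaves the same gap, but the direction cannot be stated.

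**What to change.** 1. **Section 9.1:** add BAL performed (yes/no, date of first BAL) and number of serum galactomannan tests, both taken from the medical record.
2. **Reporting:** tabulate both items by ventilation status and severity, so a reader can see whether sampling was balanced.
3. **Section 12:** add a sensitivity analysis of the risk-factor comparison with case status set by serum galactomannan ≥0,5 or proven IPA only, and/or restricted to BAL-sampled patients. With about 7 to 15 cases there is little room for extra covariates, so these are more workable than adding a BAL term.
4. **Wording:** describe ventilation and severity results as associations with diagnosed IPA, read alongside that analysis.

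Reporting of a factor should not depend on its estimate keeping direction and size in the sensitivity analysis. With a true odds ratio of 2, half the cohort ventilated and 15% IPA overall, the serum-only estimate would fail to exceed 1 in 32–47% of studies of 50 patients and 20–35% of studies of 100, so such a rule would suppress real associations.

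**Cost:** one or two CRF items and one repeated analysis, with no extra sampling. The repeated analysis will be imprecise (about 2–5 serum-based cases per 50 patients). It also leaves one source of unequal detection: serum tests run twice weekly and are no more mandatory than BAL, so a longer stay gives more chances of a positive result. Counting the serum tests makes that visible but does not remove it.
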